## 9.2.4 QC

The analysis datasets and the TFLs will be QC'd according to the PRA EDS QC plan.

### 9.2.4.1 Critical Data

The QC plan requires datasets be classified as critical or non-critical. As the primary and secondary objectives of this study are to characterize the safety and tolerability of galidesivir as well as PK profile, critical datasets include subject level demographics, PK parameters, concentrations, and AEs.

## 9.2.5 ADaM Datasets and Metadata

The analysis datasets will be generated in accordance with Clinical Data Interchange Standard Consortium (CDISC) Analysis Data Model (ADaM) Version 2.1.

ADaM-compliant datasets will be delivered to the sponsor. A define.xml file Version 2 with the corresponding metadata will be included. Analysis results metadata are excluded.

## 9.3 Software

The statistical analysis and reporting will be done using SAS® for Windows™ Version 9.4 or higher (SAS Institute, Inc.).

PK parameter calculations will primarily be done using Phoenix® WinNonlin® Version 8.1 or higher (Certara, Inc.). Additional PK computations may be performed in SAS.

## 9.4 Statistical Methods

### 9.4.1 Statistical Outlier Determination

No statistical outlier analysis is planned.

### 9.4.2 Predetermined Covariates and Prognostic Factors

There are no predetermined covariates or prognostic factors.

### 9.4.3 Hypothesis Testing

#### 9.4.3.1 Primary Objective

No formal study hypothesis will be stated or tested in this Phase I study.

#### 9.4.3.2 Secondary Objective – Dose Proportionality

Dose proportionality for  $AUC_{inf}$ ,  $AUC_t$ , and  $C_{max}$  will be evaluated using the power model (including all doses) and also using an ANOVA model where each dose will be compared with a reference dose in a pairwise basis. The mean slope from the power model and the set of pairwise comparisons from the ANOVA method will constitute descriptive evaluations of dose proportionality.

#### Power Model

The power model is as follows:

#### Equation 1:

$$\log(Y_{ik}) = S_i^{(1)} + \beta \times \log(\text{Dose}_k) + \varepsilon_{ik}$$

where  $Y_{ik}$  is the measured response variable,  $AUC_{inf}$ ,  $AUC_t$ , and  $C_{max}$ , on the  $k^{\text{th}}$  dose,  $S_i^{(1)}$  is random subject effect for the  $i^{\text{th}}$  subject, and  $\varepsilon_{ik}$  is the random error. After exponentiation, the model equation 1 is identical to equation 2 (below).

**Equation 2:**

$$Y_{ik} = \alpha \times \text{Dose}^{\beta}$$

where  $\alpha$  includes the error.

Dose proportionality for PK parameters will be assessed by restricted maximum likelihood using SAS PROC MIXED. The mean slope will be estimated from the power model and the corresponding 90% CI calculated. If the 90% CI of the slope of the  $C_{max}$  and AUCs contains 1, then dose proportionality is indicated.

**Analysis of Variance**

Following log-e transformation, dose-normalized PK parameters will be analyzed with an ANOVA model using PROC MIXED. Each dose will be compared with a reference dose on a pairwise basis. The ratio of geometric least squares means (LSM) and the corresponding 90% CI will be estimated for each PK parameter of interest. If the 90% CI for the geometric LSM ratio for a given pairwise comparison falls completely within the 0.8 to 1.25 equivalence region then dose proportionality is indicated.

**9.5 TFL Layout**

Report layout will be according to the PRA EDS standards, which are International Council for Harmonisation (ICH) E3 compliant. The layout of TFLs will be according to the PRA EDS standards.

TFL shells are provided with and approved as part of this SAP. Small changes to shell layout due to the nature of the data may be required after database lock at the discretion of the PRA project statistician. Other changes to the shells may be out of scope. The TFLs will be provided both individually in revisable text format (RTF) format, with separate files for each table, figure, and listing, and combined in Adobe PDF format. All TFLs will be in letter format.

**10.0 Analysis Populations**

Analyses	Safety Population	PK Population
Disposition Summaries	✓	
Baseline Characteristics	✓	✓
Safety Assessments	✓	
Plasma Concentrations	✓	
Plasma PK Parameters		✓
Urine PK Parameters		✓
Dose proportionality Analyses		✓

**10.1 Safety Population**

The safety population will include all randomized subjects who received any amount of study drug (ie, a partial infusion). Subjects will be analyzed according to the treatment received. This population will be used for all analyses of accountability, demographics, galidesivir drug concentration, and safety.

---

## 10.2 Pharmacokinetic Population

The PK population will include all subjects for whom at least 1 PK parameter can be estimated. The PK population will be the primary population for the PK analysis.

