7.6.3. Study Drug and Study Halting Rules

7.6.3.1. Infusion Halting Rules

For any individual subject, an infusion must be stopped for the following non-drug related events: the IV line is lost, there is extravasation, or the IV pump malfunctions such that the dose cannot be given in a controlled manner. A 10-minute window is allowed for the infusion, in order to allow for infusion issues to be resolved.

For any individual subject, the infusion must be stopped for any suspected drug-related event such as hypersensitivity (Grade 1 or higher) during infusion.

For any individual subject, the infusion must be stopped for any suspected severe (Grade 3) or serious adverse event during infusion.

The reason for subject discontinuation from the infusion will be recorded in the source documents and electronic Case Report Form (eCRF). In all cases, subjects who discontinue study drug should remain in the study and have all protocol defined study safety assessments performed.

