8.5. Replacement of Subjects

Replacement subjects may be enrolled as needed for the study to obtain the required number of evaluable subjects. An evaluable subject is defined as a subject who has sufficient PK samples collected to determine PK parameters through 24 hours post-dose and has sufficient safety data (including ECGs, ECHOs, vital signs, PE findings, and clinical lab data) through 24 hours post-dose to allow for the evaluation of the primary objective. At least 5 evaluable subjects who received galidesivir are required per cohort. Replacement subjects will be allowed if PK parameters (through 24 hours post-dose) cannot be determined due to a subject's early discontinuation from the study drug or study.

Subjects who have an IV infusion stopped for non-drug related issues, as described in Section [7.6.3.1](#), will not continue with dosing but will have all scheduled safety assessments made. These subjects may be replaced as needed. Subjects who have an IV infusion stopped for a safety related issued will not continue with dosing and will be followed as per Section [8.4.1](#). These subjects may be replaced if needed to fulfill the required number of evaluable subjects.

Subjects who withdraw due to a galidesivir-related AE will not be replaced. Subjects who withdraw for other reasons may be replaced at the discretion of the Investigator and Sponsor to ensure a sufficient number of evaluable subjects at the end of the clinical study.

Following the infusion, one subject per cohort may withdraw prior to the completion of Day 5 without being replaced. Should more than 1 subject from the same cohort who did not meet the above criteria voluntarily withdraw from the study, those subjects may be replaced.

In the event that a replacement subject withdraws, the subject will not be replaced.

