9.7. Administration

Galidesivir or placebo in LR solution will be administered IV via a peripheral venous catheter inserted into the arm of the subject. Study drug will be infused over 60 minutes via programmable infusion pump. The maximum rate expected for infusion is 8.33 mL/min. The catheter will be maintained and replaced as per institutional policies at the CRU.

An unblinded dosing team may be utilized in this study if required in order to prevent any inadvertent unblinding of study drug while connecting the masked IV bags with the infusion pumps (eg, any drips of the dosing solution during connection of the bag to the infusion pump or a temporary need to remove part of the masking tape or overlay on the IV tubing to make the connection). Members of the unblinded dosing team will not be involved in any assessments on the study and will only be utilized for dose administration. The unblinded dosing team should ensure that the study drug product is blinded to the subject and rest of the study personnel.

In the event that an infusion must be stopped in the middle of dosing for a subject, the subject will not contribute to the PK population, and will be removed from further dosing but will continue to be followed for safety assessments per protocol (Section 7.6.3). If the infusion is stopped for a non-drug related issue such as pump failure, asymptomatic extravasation, then the subject may be replaced as needed.

A physician must be present at the time of study drug administration and present in the unit for a minimum of 4 hours after completion of the infusion.

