9.8. Treatment Compliance

IV infusions of galidesivir or matching placebo in LR solution will be administered by the PI or qualified designee licensed to administer study medications. Compliance will be directly observed by study staff. Details of doses administered and dosing times will be recorded by study staff in the subject's source documentation/eCRF. Any episodes of incomplete study drug administration will be recorded.

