12.3.1.1. Analysis Populations

The analysis populations are defined below. Data from placebo-treated subjects will be pooled across cohorts.

Safety Population

The safety population will include all randomized subjects who received any amount of study drug (ie, a partial infusion). Subjects will be analyzed according to the treatment received. This population will be used for all analyses of accountability, demographics, galidesivir drug concentration, and safety.

Pharmacokinetic Population

The PK population will include all subjects for whom PK parameters can be estimated. The PK population will be the primary population for the PK analysis.

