### 3.0 Introduction

This Statistical Analysis Plan (SAP) describes the statistical methods that will be used during the analysis and reporting of data collected under BioCryst Pharmaceuticals, Inc., Protocol BCX4430-106.

This SAP should be read in conjunction with the study protocol and electronic case report form (eCRF). This version of the SAP has been developed using the protocol dated 11-Jan-2019 and the final eCRF(s) dated 30-Oct-2018.

An approved and signed SAP is a requirement for database lock.

This SAP covers all results that will be processed by the PRA Early Development Services (EDS) Biostatistics Department.

PRA EDS will perform the final pharmacokinetic (PK) and safety and tolerability analyses.

This SAP supersedes the statistical considerations identified in the protocol; where considerations are substantially different, they are identified. Any post-hoc or unplanned analyses, or substantive changes from the planned analysis in this SAP performed to provide results for inclusion in the clinical study report (CSR), will be clearly identified in the CSR. Changes to planned analyses do not require an updated SAP but should be denoted in the CSR if significant.

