## 7.0 Overview of Planned Analysis

### 7.1 Changes from Protocol

There are no changes from the protocol.

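### Protocol 9.7 takes a subject with a stopped infusion out of the PK population, but Protocol 12.3.1.1 and SAP 10.2 define that population by estimability alone

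*SAP*

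**What the plan says.** Three places decide who is in the PK population.

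- Protocol 9.7 (Administration): if "an infusion must be stopped in the middle of dosing for a subject, the subject will not contribute to the PK population". There is no exception for the cause of the stop or for estimable parameters.
- Protocol 12.3.1.1 (Analysis Populations): "The PK population will include all subjects for whom PK parameters can be estimated".
- SAP 10.2: "The PK population will include all subjects for whom at least 1 PK parameter can be estimated". This follows the protocol's definition and adds a one-parameter threshold.

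Both documents mention partial infusions, but only for the safety population. The exclusion flags in SAP 16.1.1 concern sampling-time deviations, a missing valid λz and a low R-squared. None concerns incomplete dosing, and Cmax has no flag at all.

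On precedence, SAP 3.0 says: "This SAP supersedes the statistical considerations identified in the protocol; where considerations are substantially different, they are identified". The same section asks that the SAP be read alongside the protocol. SAP 7.1 says: "There are no changes from the protocol".

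On stops, Protocol 7.6.3.1 lists the events that end an infusion and adds: "A 10-minute window is allowed for the infusion, in order to allow for infusion issues to be resolved". Under Protocol 8.5, a subject stopped for a reason unrelated to the drug "will not continue with dosing but will have all scheduled safety assessments made". Protocol 9.8 says: "Any episodes of incomplete study drug administration will be recorded".

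**The concern.** Two competent programmers could build different PK populations. One takes SAP 10.2 at its word and keeps any subject with an observed Cmax. The other carries the 9.7 rule forward and removes the subject. The choice would be made after the data exist.

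The situation can arise. Stops are mandatory for line loss, extravasation, pump failure, suspected hypersensitivity, and suspected severe or serious events. Stopped subjects stay in the study, and a plasma sample is scheduled at 30 minutes, so a stop after that point leaves a concentration from which Cmax can be read. Protocol 8.5 and 9.7 also allow replacement, so a literal SAP 10.2 could count both the under-dosed subject and the replacement.

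At stake are the PK parameter summaries of the affected cohort and the dose-proportionality comparisons that involve it.

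**Working it through.** **Which rule applies.** The plan gives no figure to reproduce here, and cohort size had no formal calculation.

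| Source | Stopped infusion, Cmax observed |
|---|---|
| Protocol 9.7 | out |
| Protocol 12.3.1.1 | in |
| SAP 10.2 | in |
| SAP 16.1.1 flags | no flag on Cmax |

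**Inputs for size.** Four cohorts of 6 on galidesivir (Protocol 7.2); criterion of a 90% CI within 0.8 to 1.25 (SAP 9.4.3.2). Cmax CVs:
- 10.6%, from the 10 mg/kg cohort report appended to the SAP. It may be understated, because three subjects exceeded the assay's upper limit.
- 25.7%, the lowest single-dose intramuscular Cmax CV in Protocol Table 3.
- 15% and 20%, assumed.

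Also assumed: one stopped infusion, fraction delivered f = 0.90, 0.75 or 0.50, true proportionality, exposure scaling with f, and the subject analysed at the assigned dose.

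**Bias if kept.** The cohort geometric mean is multiplied by f^(1/6):
- 0.90^(1/6) = 0.983, about -2%
- 0.75^(1/6) = 0.953, about -5%
- 0.50^(1/6) = 0.891, about -11%

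**Power-model slope if kept.** Slope = 1 + ln(f) × (x − x̄)/Sxx, where x = ln(dose). For 5, 10, 15 and 20 mg/kg with six subjects each, x̄ = 2.404 and Sxx = 6.505. At f = 0.50:
- subject in the 20 mg/kg cohort: 1 − 0.693 × 0.592/6.505 = 0.937
- subject in the 5 mg/kg cohort: 1 + 0.693 × 0.795/6.505 = 1.085

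**Pairwise criterion, kept versus excluded.** These are the two readings, so this is the comparison that matters. SD(ln) = √ln(1 + CV²) = 0.106, 0.149, 0.198 and 0.253. ANOVA on the log of the dose-normalised parameter, following the SAP's text, with pooled variance. Kept is 6 v 6 with 20 df; excluded is 6 v 5 with 19 df. Simulated probability that a pairwise 90% CI involving the affected cohort lies within 0.8 to 1.25:

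| CV | Excluded | Kept, 90% delivered | Kept, 75% | Kept, 50% |
|---|---|---|---|---|
| 10.6% | 91% | 93% | 80% | 14% |
| 15% | 54% | 59% | 48% | 10% |
| 20% | 16% | 20% | 16% | 3% |
| 25.7% | 2.1% | 3.1% | 2.4% | 0.6% |

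At 90% delivered, keeping gives the higher probability at every CV, because the extra subject outweighs a small bias. At 75% it is lower at the two smaller CVs, about equal at 20% and slightly higher at 25.7%. Only at 50% is it lower throughout.

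**Check by hand** (CV 10.6%, f = 0.50). Pooled SD = √[(20 × 0.1057² + 0.693² × 5/6)/20] = 0.177. Half-width = 1.725 × 0.177 × √(1/3) = 0.176. The expected interval is exp(−0.116 ± 0.176) = 0.75 to 1.06. With the subject excluded, the half-width is 1.729 × 0.1057 × √(1/6 + 1/5) = 0.111, giving 0.90 to 1.12.

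No separate AUC probability is given, because the protocol promises only safety assessments after a stop.

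**The case against.** The best reply is that the documents can be harmonised. SAP 10.2 almost repeats Protocol 12.3.1.1, and SAP 3.0 asks that the two documents be read together. The supersession clause covers statistical considerations, whereas 9.7 sits in the administration section. A specific rule normally qualifies a general one, and the statement in SAP 7.1 then fits with 9.7 staying in force. This largely stands. A reader might infer that the SAP overrides the protocol and hides the change; the text does not support that, because the tension already exists between 9.7 and 12.3.1.1. What survives is that the harmonised result has to be argued for, and nothing in SAP 10.2 or in the flags delivers it.

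The scaling assumption is also open to attack. Protocol 4.3.1.2 describes rapid initial distribution after intramuscular dosing. Under a constant-rate infusion with rapid distribution, half the infusion would produce more than half the full Cmax. The 50% column is therefore probably too pessimistic for Cmax.

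Third, the condition is narrow: a galidesivir subject, a stopped infusion and a usable sample. Two of the appended cohort reports record no subject discontinuations. That may mean discontinuation from the study rather than of the infusion, so it does not settle the matter, but neither does it suggest that a stop occurred.

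**Conclusion.** The inconsistency is real and minor. It begins inside the protocol and is inherited by the SAP, and the rule for a stopped infusion should not be left to interpretation.

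Under the stated assumptions, keeping the subject biases the cohort geometric mean by about 2 to 11% downward for 90 to 50% delivered. A reader might go further and infer that keeping the subject generally defeats the proportionality criterion. It does not: against exclusion, the chance of meeting it falls at every CV examined only when about half the dose is missing, and that result leans on a scaling assumption that is probably pessimistic for Cmax. The case for exclusion therefore rests on bias and on following the sponsor's own rule, not on the pass rate.

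There is no effect if no infusion is stopped. The objective is secondary, and SAP 9.4.3.2 calls both proportionality methods descriptive.

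**What to change.** Add one sentence to SAP 10.2: *Subjects whose infusion was stopped before completion are excluded from the PK population (Protocol Section 9.7).* Show these subjects in the already planned Listing 16.2.3. State, for this analysis purpose only, whether an infusion interrupted and then completed within the Protocol 7.6.3.1 window counts as complete. Leave the concentration summaries on the safety population, as both documents specify.

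Bring Protocol 12.3.1.1 into line with 9.7 at the next amendment. Amendments need IRB re-approval (Protocol 15.1), and the SAP sentence does not depend on one, so this can wait.

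The cost is a sentence or two, and incomplete administration is already recorded. The downside is that an affected cohort may have five rather than six galidesivir subjects in the PK population unless the subject is replaced. That number still equals the minimum of five evaluable subjects in Protocol 8.5.

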## 11.0 Subject Disposition

The number and percentage of subjects in each analysis population, who complete as well as withdraw from the study prematurely, and a breakdown of the corresponding reasons for withdrawal will be presented for the safety population. A listing of screened subjects and reasons for screen failure will also be presented.

## 12.0 Protocol Deviations

Important protocol deviations/violations will be listed as well as included in the CSR.

## 13.0 Demographic and Baseline Characteristics

### 13.1 Demographics

Subject demographics will be summarized descriptively for all subjects by cohort. The summary will include the subjects' age (in years), sex, race, ethnicity, weight (kg), height (cm), and body mass index (BMI) (in kg/m^2). Demographic characteristics will be summarized for the safety and PK populations.

All demographic data, as collected during the screening visit, will be listed by subject.

### 13.2 Medical History

Medical history will be categorized by preferred term according to the Medical Dictionary for Regulatory Activities (MedDRA) Version 21.1 and will be listed by subject.

### 13.3 Screening Results

All screening results (including eligibility criteria) will be listed by subject.

## 14.0 Prior and Concomitant Medications

Prior and concomitant medications will be categorized by medication group and subgroup according to the World Health Organization (WHO) Drug Dictionary Version September 2018 and listed by subject. Medications with an end date prior to the first dose of study drug will be considered prior medications and will be identified in the listing. Concomitant medications will include records with a start date on the same date or after the first study drug administration, and records with a start date before the date of first study medication that are indicated as ongoing. If a partial date allows a medication to be considered concomitant it will be categorized as such. Records without a start date are assumed to have started before the date of first study drug administration. Records without an end date are assumed to be ongoing.

## 15.0 Treatment Exposure

The number of subjects who receive study drug will be summarized by cohort and treatment for the safety population. All study drug administration data (including meal data indicating fasting status) will be listed by subject.

Pharmacokinetic Analyses

## 16.0 Pharmacokinetic Variables

### 16.1.1 Plasma Variables

- Plasma concentrations of galidesivir.
- Plasma PK parameters of galidesivir.

Venous blood samples will be collected to determine the plasma concentrations of BCX4430. The plasma concentration summaries and figures with mean values described in this section will be created using the safety population. The plasma PK parameter summaries and statistical analyses described in this section will be created using the PK population.

Plasma PK Parameters		
Parameter	Description	Programming Notes
AUC inf	Area under the concentration versus time curve extrapolated to infinite time, calculated as $AUC_{last} + (C_{last}/\lambda_z)$	AUCINF_obs from WNL  If valid lambda_z is not present, then parameter is flagged in listings and will not be used in summary statistics.
AUC t	Area under the concentration versus time curve from time zero to time "t"; may be denoted as AUC last if the "t" is the last timepoint with a measurable concentration	AUClast from WinNonlin If actual time deviates >20% from nominal time, then AUC t will be flagged in listings and will not be used in statistical analyses. If valid $\lambda_z$ is not present, then AUC t is flagged in listings and will not be used in statistical analyses.
% AUC exp	Percentage of AUC extrapolated between AUC last and AUC inf	AUC_%Extrap_obs from WinNonlin Listed only
C last	Last measurable concentration of drug	Clast from WinNonlin If actual time at T last deviates >20% from nominal time, then parameter is flagged in listings and will not be used in summary statistics.
T last	Time of last measurable concentration of drug	Tlast from WinNonlin If actual time at T last deviates >20% from nominal time, then parameter is flagged in listings and will not be used in summary statistics
C max	Maximum observed concentration of drug	C max from WinNonlin

Plasma PK Parameters		
Parameter	Description	Programming Notes
$t_{1/2}$	Estimate of the terminal elimination half-life of the drug	HL_Lambda_z from WinNonlin  If valid $\lambda_z$ is not present, then parameter is flagged in listings and will not be used in summary statistics.
CL	CL = Dose/AUC where "Dose" is the dose of the drug and AUC = AUC inf	CL_obs from WinNonlin
$\lambda_z$	Terminal elimination rate constant, estimate by linear regression of the terminal elimination phase of the concentration of drug versus time curve	Lambda_z from WinNonlin  If Rsq < 0.80 then parameter is flagged in listings and will not be used in summary statistics.
$V_z$	Volume of distribution of the drug	Vz_obs from WinNonlin  If valid $\lambda_z$ is not present, then parameter is flagged in listings and will not be used in summary statistics.
$T_{max}$	Time to $C_{max}$	Tmax from WinNonlin

Note: In all derivations of PK parameters, BQL values at the beginning of the profile will be set to zero, whereas BQL values that occur after the first quantifiable point will be considered missing. Samples that are BQL but are between two samples with detectable concentrations will be excluded from PK analysis.

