### 9.2.2 Treatment/Subject Grouping

Throughout this SAP, study drug refers to: BCX4430 galidesivir for IV infusion.

Label	Grouping
Study Drugs	BCX4430 galidesivir for IV infusion
Treatment	
Cohort 1:
 
 
Regimen A: Galidesivir (Dose 5 mg/kg, Calculated Dose Range 250-500 mg, Concentration 1.0 mg/mL, Dose Volume 250-500 mL), or
 
Placebo (Dose Volume 250-500 mL)
 
 
Cohort 2:
 
 
Regimen B: Galidesivir (Dose 10 mg/kg, Calculated Dose Range 500-1000 mg, Concentration 1.0-2.0 mg/mL, Dose Volume 500 mL), or
 
Placebo (Dose Volume 500 mL)
 
 
Cohort 3:
 
 
Regimen C: Galidesivir (Dose 15 mg/kg, Calculated Dose Range 750-1500 mg, Concentration 1.5-3.0 mg/mL, Dose Volume 500 mL), or
 
Placebo (Dose Volume 500 mL)
 
 
Cohort 4:
 
 
Regimen D: Galidesivir (Dose 20 mg/kg, Calculated Dose Range 1000-2000 mg, Concentration 2.0-4.0 mg/mL, Dose Volume 500 mL), or
 
Placebo (Dose Volume 500 mL)
 

Dose Levels	
BCX4430: 5 mg/kg, Calculated Dose Range 250-500 mg
 
BCX4430: 10 mg/kg, Calculated Dose Range 500-1000 mg
 
BCX4430: 15 mg/kg, Calculated Dose Range 750-1500 mg
 
BCX4430: 20 mg/kg, Calculated Dose Range 1000-2000 mg
 
[Note: Treatment labels will use mg/kg]

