## 16.2 Pharmacokinetic Summaries

### 16.2.1 Plasma Concentrations

Plasma concentrations for BCX4430 below the quantifiable limit (BQL) will be set to zero in the computation of mean concentration values. Descriptive statistics including n, arithmetic mean, SD, arithmetic CV%, geometric mean, geometric CV%, geometric n (the number of subjects with an observation who were included in the natural logarithmic transformation) median, min, and max will be used to summarize the plasma concentrations by treatment at each scheduled time point. If more than half of the subjects in a given cell have values BQL, then the descriptive statistics will not be presented and will instead display as BQL for the mean and minimum. Except for n and maximum, all other statistics will be missing. Any value less than BQL will be presented as BQL.

Linear and semi-logarithmic plots of the arithmetic mean and median plasma concentrations by scheduled sampling time will be provided by treatment. These plots will show time in hours. The plots will match the summary table results and will not have an observation at a given time point if more than half of the subjects have values BQL. Mean plots will include SD error bars when plotted on a linear scale and log scale.

Linear and semi-logarithmic plots of the individual plasma concentrations by actual sampling time will be provided by subject (1 subject per page). These plots will show time in hours. Individual plots will use the BQL handling procedure described below for "Plasma Pharmacokinetic Parameters".

All individual subject plasma concentration data will be listed by cohort and treatment.

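### Mean and median plasma concentration outputs use the safety population, so a stopped infusion would be averaged in under the full mg/kg label

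*SAP*

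**What the plan says.** SAP 16.1.1 sets the population: "The plasma concentration summaries and figures with mean values described in this section will be created using the safety population". The population grid in SAP 10.0 and the output list in SAP Appendix 3 (Table 14.2.1; Figures 14.2.4 and 14.2.5 for means, 14.2.6 for medians) say the same. So does Protocol 12.3.1.1: "This population will be used for all analyses of accountability, demographics, galidesivir drug concentration, and safety".

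SAP 10.1 defines the safety population as "all randomized subjects who received any amount of study drug (ie, a partial infusion", so a partial infusion is included by name.

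SAP 16.2.1 says that descriptive statistics "will be used to summarize the plasma concentrations by treatment at each scheduled time point". SAP 9.2.2 lists four dose levels and placebo, adds "Note: Treatment labels will use mg/kg", and has no category for an incomplete dose.

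Protocol 9.7 addresses an infusion stopped part-way: "the subject will not contribute to the PK population". It says nothing about the concentration summaries.

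The protocol foresees such stops. Protocol 7.6.3.1 requires them for loss of the line, extravasation, pump malfunction, and severe or serious events, and also says that "the infusion must be stopped for any suspected drug-related event such as hypersensitivity (Grade 1 or higher) during infusion".

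**The concern.** A mean profile labelled 10 mg/kg should describe subjects who received 10 mg/kg. As written, it would describe everyone in that cohort who received any galidesivir. Protocol 9.7 already accepts that a part-dosed subject should not represent the dose level, but its exclusion is tied to the PK population, which these outputs do not use. If 9.7 is followed, the mean curves and the parameter table for one cohort could rest on different subjects and different delivered doses.

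The plasma PK profile is the secondary objective, and each cohort has only six active subjects, so one profile carries a sixth of the weight in a mean. The SAP offers no other route for removing it: 9.4.1 plans no outlier analysis, and no section calls for a footnote or flag on a stopped infusion in these outputs.

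**Working it through.** **Stated figure.** The plan gives no number on this point, so there is nothing to reproduce. What follows is an illustration.

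**Inputs.**
- n = 6 active subjects per cohort (SAP 6.0).
- n = 7 if a stopped subject is replaced and also stays in the summary (Protocol 8.5 and 9.7 allow replacement).
- f = share of the dose delivered before the stop. The documents do not give it; an assumed range of 0.25 to 0.90 is shown.
- Concentrations after the stop are assumed to scale with the delivered dose (linear PK).

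**Formulas.** Relative to a cohort with all infusions completed:
- arithmetic mean factor = (n − 1 + f)/n
- geometric mean factor = f^(1/n)

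At f = 0.50:
- n = 6: (5 + 0.5)/6 = 0.917, a fall of 8.3%; 0.5^(1/6) = 0.891, a fall of 10.9%.
- n = 7: (6 + 0.5)/7 = 0.929, a fall of 7.1%; 0.5^(1/7) = 0.906, a fall of 9.4%.

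| f | n = 6, arithmetic | n = 6, geometric | n = 7, arithmetic | n = 7, geometric |
|---|---|---|---|---|
| 0.25 | −12.5% | −20.6% | −10.7% | −18.0% |
| 0.50 | −8.3% | −10.9% | −7.1% | −9.4% |
| 0.75 | −4.2% | −4.7% | −3.6% | −4.0% |
| 0.90 | −1.7% | −1.7% | −1.4% | −1.5% |

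In dose terms, at f = 0.50 and n = 6 the curve labelled 10 mg/kg would rest on a mean dose of (5 × 10 + 5)/6 = 9.17 mg/kg.

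**Spread.** The mean plots carry SD bars. The documents give no CV for concentrations at a time point, so 13% is assumed, close to the 12.8% reported for AUC0-24 in the interim summary of the 10 mg/kg cohort. With five full-dose subjects around 1 and one at 0.5, the variance is (4 × 0.13² + (5/6) × 0.5²)/5 = 0.0552, the SD is 0.235, and the CV is 0.235/0.917, about 26%. This is indicative only, because the input is an AUC figure.

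**Median.** Order the five full-dose values a1 to a5 and place the half-dose value below them. The median of six becomes (a2 + a3)/2 instead of a3, a shift of half the gap between two neighbouring values. The percentages above therefore do not apply to Figure 14.2.6.

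**Limits of the scaling.** A sample drawn before the stop is unaffected. One drawn soon after an early stop may lie below f times the full-dose value.

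**Does another rule remove the profile?** Analysis by treatment received (SAP 10.1) does not help, because treatment is defined by regimen and nominal mg/kg. Moving the outputs to the PK population as the SAP now defines it would not help either. SAP 10.2 admits any subject with at least one estimable parameter and omits the Protocol 9.7 exclusion, while SAP 7.1 declares no changes from the protocol.

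**The case against.** The strongest reply is that this is a deliberate and consistent choice. Protocol and SAP both put concentrations on the safety population, and showing observed concentrations in all dosed subjects, with a PK set reserved for parameters, is a recognised way to report. Nothing is hidden: incomplete administration is recorded (Protocol 9.8), dosing data are listed, each subject's profile is plotted and listed, and medians stand beside the means. That stands as far as it goes. There is no contradiction between the documents on the population, and a careful reader could trace a distorted mean. It does not make a mixed-dose mean under a single dose label correct.

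The problem is also conditional. It needs a stopped infusion and later PK samples. After a stop, Protocol 7.6.3.1 promises safety assessments and does not mention PK sampling. The legible cohort review forms report no subject discontinuations; that is not a statement that every infusion was completed, but nothing shows that one was stopped. This limit stands.

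A reader might infer that high-dose cohorts would look less than dose-proportional, because drug-related stops could cluster there. The documents do not support that. They give no stop rate by dose, and the reference to Grade 1 in the halting rule may qualify hypersensitivity alone. Dose proportionality is assessed on AUCinf, AUCt and Cmax in the PK population (SAP 10.0 and 16.2.4), not on mean curves. Whether a stopped infusion could reach those models is a separate matter of the mismatch between Protocol 9.7 and SAP 10.2.

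Finally, restricting the means to completed infusions has a price. It drops valid pre-stop samples, and it removes subjects partly on tolerability. The second matters little for a descriptive profile of a labelled dose, since these subjects stay in every safety table.

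**Conclusion.** The point holds as a minor, conditional weakness in the descriptive outputs. Followed literally, the plan averages a stopped infusion into the concentration table and the mean and median plots under the full mg/kg label, while Protocol 9.7 bars the same subject from the PK population. At the assumed half dose, the two kinds of mean at post-stop times would be roughly 7% to 11% low, depending on replacement; over the assumed range of f the effect runs from about 1% to 21%. All of this rests on one stopped infusion per cohort, continued PK sampling and linear scaling. The documents do not establish that any reported mean is wrong, that the dose-proportionality models are biased by this choice, or that protocol and SAP disagree about which population the concentrations use.

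**What to change.** - Carry the stopped-infusion exclusion of Protocol 9.7 into SAP 10.2.
- Apply the same exclusion in SAP 10.0 and 16.1.1, and in Protocol 12.3.1.1, to Table 14.2.1 and Figures 14.2.4 to 14.2.6.
- Define a stopped infusion for analysis in a way that agrees with the 10-minute infusion window in Protocol 7.6.3.1, so that a brief interruption resolved within the window is classified the same way throughout.
- Keep stopped-infusion profiles in Listing 16.2.6.1 and in the individual plots (Figures 14.2.7 and 14.2.8), flagged with the amount delivered, and footnote the summary table with the number left out.

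This needs wording changes and no new data. The affected cohort's n falls from six to five unless the subject is replaced, and valid pre-stop samples move from the summary to the listings. Fixing the rule before unblinding avoids a post hoc exclusion in a cohort of six.
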